6.1.10.3 Blood Amylase and Lipase

Tests for blood amylase and lipase will be performed during the study according to the schedule in [Table 1](#) and [Table 2](#).

6.1.10.4 Fasting Lipid Panel

Fasting lipid panel, including total cholesterol, high-density lipoprotein, low-density lipoprotein, and triglycerides, will be performed during the study according to the schedule in [Table 1](#) and [Table 2](#).

6.1.10.5 Coagulation Indicators

Tests for coagulation indicators, including prothrombin time, aPTT, and INR, will be performed during the study according to the schedule in [Table 1](#) and [Table 2](#).

6.1.10.6 Glycated Hemoglobin

Tests for glycated hemoglobin (HbA1C) will be performed as per schedule in [Table 1](#) and [Table 2](#).

6.1.10.7 Serum Pregnancy Test

Female subjects of childbearing potential (including those who have undergone tubal ligation) must undergo a serum pregnancy test within 7 days of study drug administration and record a negative result. After enrollment, serum or urine pregnancy test should be conducted according to the schedule in [Table 1](#) and [Table 2](#). Unscheduled testing can be performed if there is an indication.

6.1.10.8 Urinalysis

Urinalysis (or dipstick), including glucose, protein, ketone body, red blood cells, white blood cells, and urobilinogen, will be performed during the study according to the schedule in [Table 1](#) and [Table 2](#).

6.1.10.9 Virological Screening

Virological screening is only required if subject has finding suggestive of active viral infection and includes HIV, HBV (hepatitis B surface antigen [HBsAg], hepatitis B surface antibody [HBsAb], hepatitis B e-antigen [HBeAg], hepatitis B e-antibody [HBeAb], and hepatitis B core antibody [HBcAb]), cytomegalovirus (CMV antibody), and HCV (HCV antibody). If HBsAg or HBcAb or CMV antibody is positive, CMV DNA or HBV DNA is also required to be assayed by PCR method. If CMV DNA or HBV DNA is negative, subjects may be enrolled and their CMV DNA or HBV DNA should be monitored every cycle. If HCV antibody is positive, HCV RNA is required to undergo PCR testing. Virological screening will be performed during the Screening Period.

6.1.10.10 IDH Mutational Status

Subjects who have reports of positive IDH mutation status may directly enter the Screening phase without pre-screening. Information regarding test methodology will be collected for subjects in Part 1. Subjects who have not been tested for IDH mutations should be tested locally (via biopsy tissue collection) at the clinical trial site to determine IDH mutation status before enrollment.

Subjects will be required to provide samples for IDH mutational status confirmation as outlined in Section 6.1.14.

6.1.11 Electrocardiogram

The 12-lead ECG indicators include PR interval, QRS interval, RR interval, QT/QTcF interval, and heart rate. Evaluation time points are shown in [Appendix 1](#) and [Appendix 2](#). Unscheduled ECG or other cardiac examinations can be performed if clinically indicated.

6.1.12 Echocardiogram/Multigated Acquisition Scan

To evaluate the ejection fraction of subjects, ECHO (preferred method) or MUGA scan will be performed during the study according to the schedule in [Table 1](#) and [Table 2](#). It is recommended to use the same assessment method throughout the study for each subject.

6.1.13 Tumor Assessment

Tumor time point response assessment will be performed by the investigators according to RECIST Version 1.1 ([Appendix 8](#)) or RANO criteria for glioma subjects ([Appendix 9](#)). The tumor assessments will be performed during screening, every 8 weeks (± 1 week) beginning on C1D1 for the first 24 weeks, and every 12 weeks (± 2 weeks) thereafter as specified in [Table 1](#) and [Table 2](#), through EOT or end of Efficacy Follow-up (if applicable).

All measurable and evaluable lesions should be assessed and documented using image-based evaluation. All subjects are to be evaluated utilizing contrast-enhanced computed tomography (CT) scan or positron emission tomography (PET) scan or Gd MRI for glioma subjects to identify and follow selected lesions throughout the study. In addition, other radiographic or scintigraphic procedures (such as radionuclide bone scans), as deemed appropriate by the investigator, will be performed to assess sites of neoplastic involvement.

Tumor assessments completed as standard of care prior to signing of the informed consent but, within 28 days of first dose of study treatment, may be used as baseline scans. Assessments throughout the study should be made using the same modality as used at Screening.

6.1.14 IDH Mutation Confirmation

Samples will be collected for central confirmation of IDH mutation status in order to validate local results or reports used by sites to determine eligibility for trial. Collected samples will follow specified procedures as indicated in the laboratory manual. If archival tissue is not available, a fresh tissue biopsy will be required. This independent confirmation will use NGS, performed at a central laboratory at pre-specified intervals as determined by the Sponsor. All samples should be prepared, labeled, handled, packaged, stored, and transported in accordance with required processes as provided in the study-specific laboratory manual.

6.1.15 Pharmacokinetics and Pharmacodynamic Evaluation

6.1.15.1 Sample Collection and Handling

Blood samples will be collected for PK and PD analysis of HMPL-306 and 2-HG levels in plasma, respectively. For Cohort C-1, glioma samples will be collected during surgery for the analysis of 2-HG and HMPL-306 levels. The full PK and PD evaluation schedule is presented in [Appendix 1](#)

and in [Appendix 2](#) for Cohort C-1. Patients enrolled to the control arm of Cohort C-1 will not need to undergo PK sampling in the pre-surgery period of the study.

The collection, handling, and transportation of biological samples should be carried out in accordance with the requirements in the study-specific laboratory manual.

6.1.15.2 Analytical Procedures

Plasma samples will be analyzed to determine concentrations of HMPL-306 and 2-HG using a validated, specific, and sensitive liquid chromatography/mass spectrometry/mass spectrometry (LC MS/MS) method. Glioma tissue samples will be analyzed to determine concentrations of HMPL-306 and 2-HG using a qualified method.

Plasma samples may also be analyzed to document the presence of circulating metabolites using a qualified research method. If conducted, metabolite analysis will be reported outside of the clinical study report.

6.1.16 Exploratory Biomarker Evaluation in Tumor Specimen

Biomarkers related to HMPL-306 and solid tumors will be explored to analyze the possible correlation between biomarkers and clinical results.

Tumor tissue will be collected according to the schedule in [Table 1](#) and [Table 2](#). In the expansion part, for subjects participating in the exploratory portion of the study, at disease progression during HMPL-306 treatment or EOT, tumor tissues (formalin-fixed paraffin-embedded samples; block or 10 unstained slides, minimum tissue area, 25 mm²) will be collected to check IDH mutation status and other co-occurring gene alterations to explore the resistance mechanism of HMPL-306. For Cohort C-1, the tumor samples collected during the surgery will also be used to assess the molecular and cellular changes if the remaining sample is available after PK/PD study.

All tests are completed by the central laboratory, and all samples should be prepared, labeled, and transported according to the requirements in the study-specific laboratory manual.

6.1.17 Circulating Tumor DNA

Blood samples including ctDNA will be collected according to the schedule in [Appendix 1](#) and [Appendix 2](#). ctDNA samples will be collected at the escalation and expansion part for tumor somatic mutations (eg, CCI, etc) detection. For collection and shipping instructions, please refer to the study-specific laboratory manual. The dates of blood sampling must be recorded in the eCRF.

6.1.18 Lifestyle Management

Subjects enrolled in this study are advised to avoid unnecessary exposure to sunlight or any other source of ultraviolet light during their participation in the study and until 30 days after their last dose of study drug. Subjects are encouraged to wear sunglasses and apply sunscreen products with protective coefficient of at least SPF 15 as necessary. The safety risks of HMPL-306 under sunlight are not yet clear, and further nonclinical studies are planned to assess its photo-toxicity effects of HMPL-306.

6.1.19 End of Treatment Visit

Subjects who have completed the study or have discontinued study treatment will be asked to return to the investigational site to receive safety examinations and assessments within 7 (± 3) days after the last dose of study drug.

6.1.20 Follow-up Period

Safety Follow-up

Subjects who have completed the study treatment will be evaluated for safety 30 days (± 7) days following the EOT visit for study drug-related AEs until resolution and SAEs until resolution regardless of relationship to study treatment.

Efficacy Follow-up

Subjects who discontinue the study drug due to reasons other than disease progression, death, lost to follow-up, or withdrawal of consent will remain on study and will be followed every 12 weeks (± 14 days) from EOT visit for tumor assessment until disease progression, initiation of new anticancer therapy, withdrawal of consent, lost to follow-up, death, or the end of the study, whichever comes first.

Survival Follow-up

All subjects in expansion cohorts A, B, and D may be followed for survival status every 12 weeks (± 14 days), for a maximum of 2 years from EOT visit until death, lost to follow-up, or withdrawal of consent. Survival information can be obtained via phone, and information will be documented in the source documents and relevant eCRFs.

6.1.21 End of Study

The end of the study is defined as the date on which all subjects have their last visit or 1 year after the last subject has their first visit, whichever comes first.

6.2 Discontinuation or Withdrawal

6.2.1 Individual Subjects

6.2.1.1 Permanent Discontinuation of Treatment

The investigator has the right to discontinue a subject from the study for any medical condition that the investigator determines is in the best interest of the subject, reasons of non-compliance (eg, missed doses, visits), or pregnancy.

Any subject who discontinues treatment should be encouraged to return to the study site for an EOT visit and continue with the remaining study visits outlined in [Table 1](#) and [Table 2](#). The primary reason for discontinuation must be recorded on the appropriate eCRF.

Subjects must be discontinued from treatment for any of the following reasons:

1. Disease progression. If the subject is experiencing a treatment benefit, in the opinion of the investigator, the subject may continue study drug beyond radiographic progression until clinical progression. Determination of clinical progression is at the discretion of the

investigator and may include both objective and subjective data. The continuation decision should be made by the investigator in consultation with the Sponsor

2. Withdrawal of consent
3. Intolerable toxicity or AEs that warrant withdrawal of study treatment as determined by the principal investigator or as outlined in Section 7.4.2.
4. Poor subject compliance
5. Use of other antitumor treatment during the study
6. Pregnancy
7. Subject is lost to follow-up
8. The investigator or the Sponsor determines it is in the best interest of the subject
9. Study is terminated by the Sponsor
10. Death
11. End of this study

6.2.1.2 Withdrawal from Study

All subjects have the right to withdraw from the study at any time. During the treatment period and follow-up period, a subject who withdraws consent to continue participation in the study will not be followed for any reason after consent has been withdrawn. Every effort should be made to obtain information on subjects who discontinue study drug but who do not withdraw consent to continue participation in the study. If a participant withdraws consent for disclosure of future information, the Sponsor may retain and continue to use any data collected before such a withdrawal of consent.

All subjects who withdraw from the study may request destruction of any samples taken and not tested, and the investigator must document this in the site study records.

6.2.1.4 Subjects Lost to Follow-up

A subject will be considered lost to follow-up if he or she repeatedly fails to return for scheduled visits and is unable to be contacted by the study site.

Before a subject is deemed lost to follow up, the investigator or designee must make every effort to regain contact with the subject (where possible, 3 telephone calls and, if necessary, a certified letter to the subject's last known mailing address or local equivalent methods). These contact attempts should be documented in the participant's medical record.

Should the subject continue to be unreachable, he/she will be considered withdrawn from the study.

CCI

CCI

7 STUDY INTERVENTIONS

7.1 Study Drug Administration

Subjects will receive dosing of HMPL-306 PO, QD, in each 28-day cycle.

Subjects should take HMPL-306 on an empty stomach (defined as no food ± 2 hours of dosing) at a relatively fixed time every day, with about 240 mL of water. The accurate actual time of dosing should be recorded in the subject diary each time.

7.1.1 Part 1 (Dose Escalation)

In dose escalation, dosage will be according to dose level (see [Table 5](#)).

Dose escalation will begin at [REDACTED] mg QD of HMPL-306 in a 28-day continuous dosing treatment cycle. The dose will escalate successively according to the sequence of [REDACTED] mg QD, [REDACTED] mg QD, [REDACTED] mg QD, [REDACTED] mg QD, [REDACTED] mg QD, [REDACTED] mg QD, and [REDACTED] mg QD.

7.1.2 Part 2 (Dose Expansion)

In dose expansion, HMPL-306 will be administered PO, QD, in a 28-day continuous dosing treatment cycle at MTD and/or RP2D.

7.2 Description of Products

HMPL-306 will be provided as a tablet formulation in 2 strengths: [REDACTED] mg and [REDACTED] mg.

7.2.1 Formulation, Storage, Preparation, and Handling

HMPL-306 is formulated as tablets, which are packaged in high-density polyethylene bottles, with 30 tablets per bottle. The contents of the label will be in accordance with all applicable regulatory requirements.

HMPL-306 should be sealed and stored in a secure, limited access area under appropriate conditions. The storage temperature should be between [REDACTED] °C to [REDACTED] °C with [REDACTED]. HMPL-306 should not be used beyond the expiration date provided by the manufacturer.

The temperature-monitoring log should be recorded and filed in the study binder.

7.2.2 Drug Accountability

7.2.2.1 Assignment/Disposal (Study Site)

All study drug required for this study will be provided by the Sponsor. The recipient will acknowledge receipt of the drug by returning the appropriate documentation form indicating shipment content and that condition supplies will be replaced.

Accurate records of all study drug received at, dispensed from, returned to, and disposed of by the study site should be recorded by using the Drug Inventory Log.

Study drug will be disposed of at the study site according to the study site's institutional standard operating procedure or will be returned to the Sponsor or designee with appropriate

documentation, as determined by the study site. If the study site chooses to destroy study drug, the method of destruction must be documented.

7.2.2.2 Drug Return (Subject)

On Day -2 to Day 1, only drug assignment will be performed. The first dose of study drug should be administered on C1D1. Subjects will be provided with a pill diary and will be instructed on how to account for each day's dose appropriately. Subjects should return all unused study drug and containers from the previous cycle on Day 1 (date of scheduled visits) of each subsequent cycle, and the new study drug will be dispensed on the same day. Site study staff should review subject's pill diary and provide a new diary if necessary at the Day 1 visit of each cycle.

If a dose adjustment is required, the subject must return to the investigational site and return all unused study drug. The site must log into the eCRF, adjust the dose, reassign the drug serial number, and dispense new study drug dose to the subject. If the dose is adjusted a second time, the site must log into the eCRF and record the second dose adjustment. On this occasion, it is not necessary to reassign a new drug serial number. If tumor evaluation shows PD during the previous cycle and the new drug has been dispensed, the subject must return all unused study drug on the 30-day safety visit after EOT.

7.3 Assessment and Verification of Compliance

The investigator is responsible for ensuring the subject's treatment compliance. The Sponsor will provide supervision through on-site monitoring visits made by its representatives. The investigators should maintain complete and accurate records of drug use. The dosing regimen and subject's actual dosing should be recorded in the original treatment records, as well as eCRF. At each treatment visit, the investigators or study staff should comprehensively assess the subject's treatment compliance according to the drug dispensing and return status at each visit and the actual dosing conditions, such as missed doses and overdosing reported by the subject. The subjects must return all drug bottles and remaining capsules at the end of the study. The investigational sites must return all remaining supplies and drugs to the Sponsor or provide evidence of destruction at the conclusion of the study.

7.4 Dose Adjustments

7.4.1 Adjustment of Dose within the DLT Assessment Window

In the DLT assessment window, subjects without DLT must not undergo dose reduction of HMPL-306.

- If a DLT occurs, HMPL-306 administration will be suspended and appropriate supportive treatment will be given
- If a DLT returns to Grade 1 or lower within 14 days, HMPL-306 may be resumed at the previous lower dose if the investigator assesses that the subject may still benefit
- If a DLT has not returned to Grade 1 (inclusive) or lower within 14 days, or DLT reoccurs at the lowered dose, HMPL-306 will be terminated

- If the subject has an AE that does not meet the DLT criteria, the subject should continue HMPL-306 according to the original planned dose; for Grades 3 and 4 non-DLT AEs, HMPL-306 can be suspended as necessary as assessed by the investigator

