7.4.3 Dose Adjustment for QT Interval Prolongation

Table 9 Dose Adjustment for QT Interval Prolongation

Degree of QTcF Prolongation	Action
QTcF >480 ms to 500 ms	
 Hold drug. Monitor and supplement electrolyte levels as clinically indicated. Review and adjust concomitant medications with known QTcF interval-prolonging effects. Restart HMPL-306 at original dose if QTcF interval returns to ≤ 480 ms. Monitor ECGs at least weekly for 2 weeks following resolution of QTcF prolongation.
QTcF >500 ms	
 Hold drug. Monitor and supplement electrolyte levels as clinically indicated. Review and adjust concomitant medications with known QTcF interval-prolonging effects. Restart HMPL-306 at half of the original dose when QTcF interval returns to within 30 ms of baseline or ≤ 480 ms. Monitor ECGs at least weekly for 2 weeks following resolution of QTcF prolongation. Consider re-escalating HMPL-306 to the original dose if an alternative etiology for QTcF prolongation can be identified.
QTcF interval prolongation with signs/symptoms of life-threatening arrhythmia	
 Discontinue HMPL-306 permanently.

ECG = electrocardiogram; QT = interval from the start of the Q wave to the end of the T wave; QTcF = QT interval corrected for heart rate using Fridericia's formula.

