7.4.4 General Dose Adjustment Note

The severity of DLTs/AEs will be graded according to the National Cancer Institute Common Terminology Criteria for Adverse Events (NCI CTCAE) Version 5.0. Reasons for dose modifications or delays, the supportive measures taken, and the outcome should be documented in the subject's chart and recorded in the eCRF.

- For any concomitant conditions already apparent at baseline, the dose modifications will apply according to the corresponding shift in toxicity grade, if the investigator feels it is appropriate. For example, if a subject has Grade 1 asthenia at baseline that increases to Grade 2 during treatment, this will be considered a shift of 1 grade and will be treated as Grade 1 toxicity for dose modification purposes
- For toxicities that are considered by the investigator to be unlikely to develop into serious or life-threatening events, treatment can be continued at the same dose
- To recover from acute toxicity, unless otherwise indicated, the treatment can be delayed for up to 14 days. If a treatment delay longer than 14 days is required, treatment should be

discontinued. Continuation/resumption of treatment after an interruption of more than 14 days must be discussed with the medical monitor or his or her designee

- Where several toxicities with different grades or severity occur at the same time, the dose modifications should be according to the highest grade observed

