8.1.3 Dose-Limiting Toxicity

DLT is defined as the occurrence of any of the following TEAEs during the DLT assessment window, unless the TEAEs are clearly unrelated to the study drug or judged by the investigator as not clinically significant.

1. Non-hematologic toxicities:
 - Any Grade 4 non-hematologic toxicity
 - Grade 3 non-hematologic toxicity, except for the following conditions:

- Recovered to Grade ≤ 1 within 3 days after supportive therapy is administered for nausea, vomiting, diarrhea, constipation, fatigue, and electrolyte imbalance
 - Grade 3 hypothyroidism, adrenal gland or pituitary insufficiency, and inflammatory reactions at the tumor site
 - Grade 3 hypertension downgraded to Grade ≤ 1 within 1 week with appropriate supportive therapy
2. Hematologic toxicity:
- Grade ≥ 3 febrile neutropenia (neutrophil count $< 1.0 \times 10^9/L$, accompanied with a single body temperature measurement of $\geq 38.3^\circ C$ or $\geq 38^\circ C$ persisting for 1 hour)
 - Grade 4 neutropenia
 - Grade 4 thrombocytopenia
 - Grade 3 thrombocytopenia accompanied with clinically significant bleeding, in addition to that requiring transfusion
 - Grade 4 anemia requiring a dose delay of ≥ 14 days
3. Any life-threatening complication or abnormality not covered in the NCI CTCAE Version 5.0.

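### Within the DLT window, Protocol Section 7.4.1 and Table 9 conflict on dosing after QTcF prolongation that is not a DLT (above 500 ms; also above 480 to 500 ms if that is below Grade 3), and no visible text says which governs

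*Protocol*

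**What the plan says.** Protocol Section 7.4.1 governs dosing during the DLT window (C1D1 to C1D28, Part 1 only). Its opening rule is: "In the DLT assessment window, subjects without DLT must not undergo dose reduction of HMPL-306". For events short of a DLT it adds: "If the subject has an AE that does not meet the DLT criteria, the subject should continue HMPL-306 according to the original planned dose". The one relaxation is that "for Grades 3 and 4 non-DLT AEs, HMPL-306 can be suspended as necessary as assessed by the investigator".

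Table 9, in Section 7.4.3, is triggered by the measured QTcF and mentions neither DLT status nor CTCAE grade:

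- Above 500 ms: hold, then "Restart HMPL-306 at half of the original dose when QTcF interval returns to within 30 ms of baseline or" is at or below 480 ms. Afterwards: "Consider re-escalating HMPL-306 to the original dose if an alternative etiology for QTcF prolongation can be identified".
- Above 480 to 500 ms: hold, then "Restart HMPL-306 at original dose if QTcF interval returns to" 480 ms or less.
- Prolongation with signs or symptoms of life-threatening arrhythmia: stop permanently.

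The Section 7.4.2 heading confines Tables 7 and 8 to time outside the DLT window. The Section 7.4.3 heading carries no such limit.

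Section 8.1.3 leaves a route by which a marked QTcF prolongation is not a DLT. Listed events count "unless the TEAEs are clearly unrelated to the study drug or judged by the investigator as not clinically significant".

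Section 7.4.4 adds that for toxicities the investigator considers "unlikely to develop into serious or life-threatening events, treatment can be continued at the same dose".

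**The concern.** On the visible text both sections apply in Cycle 1 of Part 1, and for some QTcF events they direct opposite actions. QTcF prolongation is a named potential risk in Table 3, described there as a class effect of approved IDH inhibitors. A site that follows 7.4.1 to the letter would leave out a QTcF precaution that the protocol itself prescribes. A site that follows Table 9 would breach an explicit prohibition on dose reduction. Different sites could reasonably choose differently, during the period in which each new dose level is first tested.

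**Working it through.** The plan gives no figure to reproduce. The check is a comparison of the rules, followed by arithmetic on what each choice does to DLT evaluability.

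**Step 1. Instructions side by side (Cycle 1, event not a DLT).**

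| Situation | Section 7.4.1 | Table 9 | Both possible? |
|---|---|---|---|
| QTcF above 500 ms: hold | Optional if Grade 3 or 4; otherwise continue | Required | Yes, if Grade 3 or 4 |
| QTcF above 500 ms: restart dose | 100% of planned | 50% of planned | No |
| QTcF above 480 to 500 ms, if below Grade 3 | Continue at planned dose | Hold | No |
| QTcF above 480 to 500 ms, if Grade 3 | May suspend | Hold, restart at full dose | Yes |

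No conflict is claimed for the arrhythmia row. So two of the three Table 9 rows are affected, and the second only under the grade assumption. In that second row the restart is at full dose, so the no-reduction rule is not breached. Only the hold is at issue.

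**Step 2. Is there a tie-breaker?** Section 7.4.4 is permissive, covers only toxicities judged unlikely to become serious, and mentions neither the window nor Table 9. For such events it agrees with 7.4.1, but it does not rank the two. The SAP leaves the DLT-evaluable set to medical and Safety Review Committee (SRC) review (Sections 3.1.3 and 7) and contains no dosing rule. Some protocol text is redacted, so this holds for the visible text only.

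**Step 3. How often could it arise?** Exclusion criterion 10 removes subjects with QTcF of 470 ms or more. Section 4.1.1 reports no DLTs or safety concerns at levels 1 to 4. Appendix 1 schedules ECGs in the window at predose, 1, 2 and 4 h on C1D1. That is three post-dose time points, with none from C1D2 to C1D28; the next is C2D1 (day 29). Later detection in the window needs an unscheduled ECG, which Section 6.1.11 allows. The documents give no QTcF event rate.

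**Step 4. Effect on evaluability.** Section 4.1.1 requires 75% of the assigned dose in the window, unless the subject stopped for a DLT. Taking the assigned dose as the cohort dose, 0.75 × 28 = 21 full-dose equivalents, so at most 7 may be missed.

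Share received = (full-dose days + 0.5 × half-dose days) / 28. The subject stays evaluable when held days + 0.5 × half-dose days ≤ 7.

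- Above 500 ms on C1D1, held 1 day, half dose for the other 26 days: (1 + 0.5 × 26)/28 = 14/28 = 50.0%, not evaluable.
- The same with a 7-day hold: (1 + 0.5 × 20)/28 = 11/28 = 39.3%, not evaluable.
- The same subject continued without interruption under 7.4.1: 28/28 = 100%, evaluable without a DLT.
- Above 480 to 500 ms, 7-day hold, then full dose: 21/28 = 75.0%, evaluable. With an 8-day hold: 20/28 = 71.4%, not evaluable.

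**The case against.** The strongest reply is that a sensible site would read the QT-specific table as the exception to the general rule. That is plausible, but it is inference: 7.4.1 is just as specific to the window, and its prohibition is worded as mandatory.

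Second, the firm case is narrow. It needs Part 1, Cycle 1, QTcF above 500 ms and a judgement that the event is clearly unrelated or not clinically significant. For an unrelated event another cause will often have been found, and Table 9 then suggests considering a return to full dose. What remains in dispute is an interim half-dose restart. This stands, and it limits the size of the point. It does not remove the contradiction, because Table 9 speaks of re-escalation and so presupposes that the dose was already halved.

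Third, the 480 to 500 ms case depends on a grade cut-point that is not in the documents. This also stands, and that part is therefore conditional.

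A reader might infer that Table 9 plainly takes precedence, because Amendment 1 added it at the FDA's request, or because Table 3 says QTcF is monitored for the whole study. Neither settles it. The same amendment added Tables 7 and 8, also at the FDA's request, and those sit under the outside-window heading. The Table 3 phrase describes monitoring, not the scope of the dosing rule. Both are supportive only.

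Finally, the text may be out of date. The SAP is based on Amendment 3, which is not among the documents, and Section 1 of the SAP says the study did not proceed to expansion.

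**Conclusion.** The contradiction is real but minor. For a non-DLT QTcF above 500 ms in Cycle 1 of Part 1, 7.4.1 forbids the half-dose restart that Table 9 requires. The hold itself can be reconciled if the event is Grade 3 or 4. For QTcF above 480 to 500 ms the rules conflict on the hold only on the assumption that this range is below Grade 3; if it is Grade 3, there is no conflict.

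A reader might infer from the evaluability arithmetic that the ambiguity distorts dose-escalation decisions or the MTD. The documents do not support that: they give no QTcF event rate, and the entry criterion and the experience at levels 1 to 4 suggest few such events. Nor do they show that any subject was dosed wrongly.

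**What to change.** First check whether the wording persists in Amendment 3. If it does and Part 1 dosing is still open, add to Section 7.4.1:

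*For QTcF prolongation within the DLT window that does not meet the DLT criteria, the Table 9 hold and restart-dose rules apply, as an exception to the no-reduction and continue-as-planned rules. QTcF events that are DLTs remain subject to the DLT suspension, Grade 1-or-lower within 14 days, and termination rules above, and to permanent discontinuation under Table 9 for signs or symptoms of life-threatening arrhythmia.*

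The second sentence matters. Letting Table 9 govern every QTcF event in the window would loosen the DLT rule. Section 7.4.1 requires recovery to Grade 1 or lower within 14 days or termination. Table 9 allows a restart at 480 ms or less, or within 30 ms of baseline above 500 ms, and states no time limit of its own. The general 14-day limit in 7.4.4 would remain, but it allows resumption after discussion with the medical monitor.

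The cost is two sentences of protocol text and an occasional subject who falls below 75% of the assigned dose and is replaced under Section 6.2.1.3, adding one subject and one 28-day window each time. The 75% and replacement rules stay as they are. No SAP change is needed: Sections 4.4.3 and 5.2.11.5 already plan counts of QTcF above 480 and above 500 ms and a listing of all ECG data.

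If Part 1 dosing is complete, the remaining action is to check which rule was followed for any Cycle 1 QTcF above 480 ms.
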